1.3. Schedule of Activities (SoA)

Period	Screening	Baseline	Double-Blind Treatment					No Treatment	Notes	
			1 (first dose)	14±3	28±3	42±3	84±3 End of Treatment			
Day	Within 28 days before Baseline	Within 7 days before Day 1	1					252→7 End of Study	Day -28 to 0=Screening; Day 1 = first dose, Day 84= end of treatment; Day 252=End of Study	
Week			1	2	4	6	12		Week 12 is equivalent to Day 84 of treatment	
Month		0					3	9	Month 3 is equivalent to Day 84 of treatment	
Study Procedure										
Screening/Administrative										
Electronic Informed consent ^a	X									
Review medical history	X									
Inclusion/exclusion criteria ^b	X	X							All inclusion/exclusion verification should be completed within the 28-day screening period and before randomization	
KCCQ baseline overall summary score ≤80		X								
Study Intervention Administration										
Randomization		X								
Dispense study intervention		X								
Administer study intervention		←								
Participant-reported adherence via app - weekly		←								
Assessments										
KCCQ			X	X	X	X	X	X ^c	X	Kansas City Cardiomyopathy Questionnaire
PGIC			X	X	X	X	X	X ^c	X	Patient Global Impression of Change
PGI-S		X	X	X	X	X	X	X ^c	X	Patient Global Impression of Severity
Step count and floors climbed		←							←	
Medical claims data collection ^d		←							←	
Participant Satisfaction Survey (optional)									X	

Period	Screening	Baseline	Double-Blind Treatment					No Treatment	Notes
Day	Within 28 days before Baseline	Within 7 days before Day 1	1 (first dose)	14+3	28±3	42±3	84±3 End of Treatment	252±7 End of Study	Day -28 to 0=Screening; Day 1 = first dose, Day 84= end of treatment; Day 252=End of Study
Week			1	2	4	6	12	13-36	Week 12 is equivalent to Day 84 of treatment
Month		0				3	6	9	Month 3 is equivalent to Day 84 of treatment
Health Resource Utilization and Health Economics									
HHF for any reason and duration		←	←					→	Hospitalizations for heart failure
Emergency department visits		←	←					→	
Readmissions and duration		←	←					→	
Ongoing Review of Participant Data									
Prohibited medications and new diagnoses		←	←					→	
Reporting of adverse events ^e	←	←	←					→	

Footnotes:

- a. Must be signed before first study-related activity.
- b. Minimum criteria for the availability of documentation supporting the eligibility criteria are described in Source Documentation in Section 10.2, Appendix 2: Regulatory, Ethical, and Study Oversight Considerations.
- c. To be completed at Month 6.

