Due to the virtual method of data collection for this study, there will be 2 types of adverse event data collection, one by participants instructed to self-report any adverse events to a call center, and the other by an analysis of medical claims data from the participant's provider to their insurance system. Participant-reported adverse events to the call center will be captured from the time of informed consent until 30 days after the end of treatment (ie, the last dose of study intervention) and adverse events from medical claims data from the time of informed consent to the end of study.

After the treatment period plus 30 days, serious adverse events will be identified solely through medical claims data. Adverse events that occur during the treatment period plus 30 days identified from medical claims will be aggregated by treatment assignment when unblinding is available. In addition, for this time period, self-reported adverse events from the call center will be summarized in a listing. Serious adverse event data from medical claims for the 9-month study period will be aggregated by treatment assignment.

HYPOTHESIS

The primary hypothesis is that canagliflozin is superior to placebo as assessed by improvement in the TSS on the KCCQ scale during the 3-month, double-blind treatment period.

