4.4. End of Study Definition

A participant will be considered to have ended the treatment period of the study (at 3 months), regardless of whether the participant has completed the study intervention, if he or she has completed assessments at Month 3 of the double-blind treatment period, withdrew earlier from the treatment, or died prior to the Month 3 assessment.

The end of study (at 9 months) is considered as the last visit shown in the Schedule of Activities for the last participant in the study. The final data from the study clinical research organization

partner will be sent to the sponsor (or designee) after completion of the collection of the study data from the Fitbit device and the claims in the time frame specified in the Trial Agreement.

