1.6. Study Data Flow

Data flow in this study is facilitated by an automated integrated process that extracts clinical data from 3 sources: PRA mobile health platform [PRA mHP], Care Innovations, and Symphony. These data are loaded into PRA's Common Clinical Data Store (CCDS) where the data is accessible by JReview for data validation and analysis, as well as for extraction into RAW and SDTM datasets. This automated Extract-Transform-Load (ETL) process will utilize a data container on Amazon Web Services (AWS), referred to as the "Data Analytics Container" or "DAC", which is managed by PRA. A more detailed data flow diagram is provided in Appendix 5 of this SAP.

The PRA mHP platform serves as the main hub for source data capture on the CHIEF-HF study. It captures eConsent, information entered by Health Network Systems (HNS) from a participant's electronic medical records (EMRs), participant status overseen by Care Innovations (CI), randomization through integration with Endpoint IRT, drug shipment through integration with Marken, primary and secondary endpoint data from ePROs (KCCQ, PGI-S, PGIC), dosing compliance, as well as activity measured by the Fitbit watch. PRA mHP data will go into the DAC via a direct database connection. Medical and pharmacy claims data is contained within Symphony

Health Solutions and exists as completely de-identified data. This includes data used in the study to review and analyze adverse events, healthcare resource utilization (HRU) and health economics (including hospitalization/readmission due to Heart Failure [HF] or other reason, Emergency Department (ED) visits, the duration of stay at each hospitalization/readmission), as well as review of prohibited medications and new diagnoses that may require discontinuation.

Symphony claims data will be pulled into the DAC for participants randomized into the study via PRA mHP eConsent and will be mapped to SDTM as detailed in the SDTM specifications relevant to the study protocol and SAP. The collection timeframe for claims associated with AEs of special interest will begin on the Informed Consent Date through the End of Treatment + 30 days. The collection timeframe for Pharmacy claims of prohibited concomitant medications (SGLT2i) will begin on the ICF date through End of Treatment. The collection timeframe for claims associated with Health Resource Utilization will begin on the ICF Date through the 9-month observation period.

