Daily activity measurements via the Fitbit device will be collected continuously from the time study started (ie, when both the smartphone and the Fitbit are linked by a participant). Fitbit daily activity data will be aggregated into averages over 2-week intervals starting with a baseline period (ie, Baseline = average of Study Day 1 to Study Day 14) and similarly over the entire post-baseline study duration for each participant. This is to allow capturing a robust length of physical activity for each participant using the Fitbit device and minimizing variability associated with measurements in shorter time spans. The end-of-treatment (EOT) average value of the step count will be the average of the last 14 days prior to the last dose of study intervention, regardless of when the last dose is taken.

Claims data will be extracted as access to participant-level information becomes available. This will include clinical outcomes (including hospitalizations for HF and/or other reasons) coded using International Statistical Classification of Diseases and Related Health Problems (ICD)-9 and ICD-10 as appropriate.

Time windows will not be applied to summarize the safety data collected through claims. Self-reported safety data will be summarized through Week 12 (Day 87).

Table 1 presents the time windows and the target days for each time of measurement defined in the protocol.

Table 1: Measurement Windows

Parameter	Time Interval (label on output)	Time Interval (Day)*	Target Time Point (Day)
KCCQ (and its individual domains); PGIC and PGI-S; participant satisfaction survey	Screening/Baseline	-21 to <1	1
	Week 2	11 to 17	14
	Week 4	25 to 31	28
	Week 6	39 to 45	42
	Week 12	81 to 87	84
	Month 6	161 to 175	168
	Month 9	245 to 259	252
Daily Step Count / Daily Floors Climbed **	Baseline to Week 2	1 to 14	
	Week 3 & Week 4	15 to 28	
	Week 5 & Week 6	29 to 42	
	Week 7 & Week 8	43 to 56	

Parameter	Time Interval (label on output)	Time Interval (Day)*	Target Time Point (Day)
	Week 9 & Week 10	57 to 70	
	Week 11 & Week 12	71 to 84	
	
	Week 35 & Week 36	238 to 252	

*Relative to Study Day 1

** Measurements over a 2-week interval with ≥ 100 daily steps to allow capture of physical activity

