Baseline for daily step count and daily floors climbed variables will be defined by averaging the daily values over a 14-day interval starting with the first dose date. These data will be organized into a vertical file format to read one record per participant for averages over each 2-week interval during the entire study (including the EOT/EOS values, as applicable).

Claims Data – AEs, HRUs, Clinical Outcomes

Claims data pertaining to AEs of interest (as defined in the protocol), number of prescription fills, HRUs, and clinical outcomes reported with appropriate ICD codes applied at the individual participant level will be organized with one record for each incident (ie, hospitalization, etc.) date. Adverse events of interest include all severe hypoglycemic events, acute kidney injury, fractures, diabetic ketoacidosis, and lower limb amputation.

In addition, the following adverse events will be examined: hypotension; Fournier’s gangrene; genital mycotic infections; urinary tract infections (including urosepsis and pyelonephritis); increased urination; and hypersensitivity reactions including angioedema and anaphylaxis.

Self-reported AE data – Data from participants self-reporting adverse events (AEs) to a Call Center (set up by Care Innovations) will be manually submitted directly to the Sponsor (i.e. Janssen Safety [GMS]) for appropriate evaluation and analysis. Janssen Safety (GMS) will extract participant-reported AEs and transfer data to PRA for upload into the CCDS. Self-reported events will be captured from the date of the first dose of study intervention through the end of treatment (Month 3) plus 30 days. A listing of these self-reported AE may be produced based on available data.

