6.1. Adverse Events

All AE data summaries will be based on the safety analysis set except where stated otherwise. A treatment emergent AE is defined as an event that occurs after the first dose of study intervention (Study Day 1) and/or worsens in severity during the double-blind treatment period.

Adverse events self-reported to the Call Center will be assessed by Janssen Global Medical Safety (GMS) for start and end dates, causality and meeting SUSAR reporting requirements. If the specific dates pertaining to the self-reported AEs are unknown, there will be limited follow-up for resolution. For any events still ongoing at the end of the study, there will be no follow up (as the Call Center will be closed at that point) possible. Adverse events will be coded according to MedDRA and will be reported by preferred term for each randomized intervention group. Janssen Data Management will request a listing of all AEs/SAEs reported to the Call Center from the Janssen GMS. This listing will be shared with PRA (external vendor) to convert the information

into the SDTM format and for inclusion in the final SDTM data package for summary by various subgroups (e.g., T2DM and non-T2DM).

Adverse events collected through the claims database will be analyzed separately for the 12-week treatment period + 30 days after last dose and the 9-month entire study period respectively. It is assumed that claims database will have dates of service provided (procedure dates, office visits, hospital admissions, etc.) but not actual start/end dates of events prior to claims being filed. Therefore, no imputation of AE start/end dates will be feasible based on the claims data. Dates of service(s) rendered to participants during the study (i.e., starting from the time informed consent is signed until the end of double-blind treatment plus 30 days) will be taken into account. The claims data will utilize ICD codes to identify the SAEs and AEs of interest which are defined in the protocol and for the final analysis. The AEs of interest include all severe hypoglycemic events, acute kidney injury, fractures, diabetic ketoacidosis, and lower limb amputation. In addition, hypotension, Fournier's gangrene, genital mycotic infections, urinary tract infections (including urosepsis and pyelonephritis), increased urination and hypersensitivity reactions (including angioedema and anaphylaxis) will be considered for coding and final analysis.

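### The treatment-period adverse-event window has conflicting end dates; if it is programmed as last dose plus 30 days, early stoppers lose up to 83 of 114 days and by-arm percentages compare unequal follow-up

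*SAP*

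**What the plan says.** **Self-reports to the call center.** Protocol 3 captures events "until 30 days after the end of treatment (ie, the last dose of study intervention"; the Synopsis and footnote e of the Schedule of Activities (1.3) use the same anchor. SAP 5.1.2 instead captures them "through the end of treatment (Month 3) plus 30 days". SAP 2.1 adds a third end: "Self-reported safety data will be summarized through Week 12 (Day 87".

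**Claims.** SAP 6.1 analyzes events over the "12-week treatment period + 30 days after last dose" and, separately, over the full 9 months. The same paragraph takes service dates "until the end of double-blind treatment plus 30 days", with no mention of last dose. SAP 1.6 says that collection of claims for events of special interest "will begin on the Informed Consent Date through the End of Treatment + 30 days", without defining end of treatment. The protocol (Synopsis, 3 and 8.3.1) speaks only of the treatment period plus 30 days for the by-arm claims summary, although it captures claims events to the end of the study.

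**What end of treatment means.** The Schedule of Activities fixes "Day 1 = first dose, Day 84= end of treatment; Day 252=End of Study". SAP 2.6, however, ties the end-of-treatment observation to each participant's actual last dose. Protocol 4.4 also treats a participant as having ended the treatment period if he or she "withdrew earlier from the treatment, or died prior to the Month 3 assessment".

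**How events are reported.** SAP 6.1 gives numbers and percentages of participants with an event by randomized group and diabetes status, for both periods. No exposure-adjusted rate is planned.

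**The concern.** For someone who takes drug to Day 84, the last-dose and Month 3 anchors coincide. They separate only for participants who stop early. Two programmers could therefore build different by-arm tables, each with support in the text.

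The choice matters because the summaries are crude percentages. If more participants stop early in one arm, the last-dose anchor gives that arm less observation time, and nothing in the table shows it. Stopping is also linked to safety. Protocol 7.1 lists adverse events among the reasons for stopping drug, including ketoacidosis and amputation, which are also events of interest in Protocol 8.3.4. The lost days may therefore come from participants whose later risk is not average.

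**Working it through.** The plan states no figure for days lost, so there is none to reproduce.

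**Inputs.** End of treatment is Day 84, with Day 1 the first dose (Protocol 1.3), and the visit window is ±3 days. The extension is 30 days. One dose is enough to enter the safety set (SAP 2.3.4), so the earliest last dose is d = 1.

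**Date arithmetic.** The fixed end is 84 + 30 = Day 114. The last-dose end is Day d + 30. Days lost = 114 - (d + 30) = 84 - d.

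| Last dose (d) | Window ends (d + 30) | Days lost (84 - d) | Share of 114 days |
|---|---|---|---|
| 1 | 31 | 83 | 72.8% |
| 14 | 44 | 70 | 61.4% |
| 20 | 50 | 64 | 56.1% |
| 28 | 58 | 56 | 49.1% |
| 42 | 72 | 42 | 36.8% |
| 56 | 86 | 28 | 24.6% |
| 84 | 114 | 0 | 0% |

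If nominal end of treatment falls at Day 81 or Day 87, the maximum is 80 or 86 days.

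**The Day 87 rule for self-reports.** Against Day 114 it removes 114 - 87 = 27 days even from a completer. It ends before the last-dose window whenever d + 30 > 87, that is, d > 57.

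**Illustration of the effect on a by-arm percentage.** The documents give no stopping rates or event risks, so every input here is an assumption: a 10% risk over 114 days at constant hazard h = -ln(0.9)/114, stopping at Day 20, and hazard m × h afterwards. Non-stoppers have a 10% risk. A stopper's risk is 1 - exp(-h × E), where E = 20 + 94m under the fixed window and E = 20 + 30m under the last-dose window. An arm's percentage is (1 - p) × 10% + p × the stopper's risk, with p the proportion stopping.

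| m | Stopping, active / placebo | Fixed window, difference | Last-dose window, difference |
|---|---|---|---|
| 1 | 10% / 5% | 0 | 9.45% - 9.73% = -0.27 |
| 1 | 20% / 10% | 0 | 8.90% - 9.45% = -0.55 |
| 3 | 10% / 5% | 11.44% - 10.72% = +0.72 | 9.97% - 9.98% = -0.02 |
| 3 | 20% / 10% | 12.87% - 11.44% = +1.44 | 9.93% - 9.97% = -0.03 |
| 5 | 10% / 5% | +1.32 | +0.23 |

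Differences are in percentage points, taken before rounding. In every row the last-dose window moves the comparison in favor of the arm that stops more. The near-zero result at m = 3 is a coincidence of inputs: 20 + 3 × 30 = 110 hazard-days, close to the 114 of a non-stopper.

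**Is the 9-month table a backstop?** It does not depend on last dose, and it adds 252 - 114 = 138 days after Day 114. SAP 6.1 promises events of interest over that period, but SAP 1.6 pulls their claims only to end of treatment plus 30 days. Both cannot hold. Claims for resource use are pulled for the full 9 months, so hospitalizations should be available; outpatient events of interest might not be.

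**The case against.** The strongest reply is that this is a wording matter. SAP 6.1 can be read as a full 12 weeks plus 30 days, since a 12-week period has a fixed length and the service-date sentence in that paragraph does not mention last dose. On that reading no claims days are lost. A second by-arm table covers all 9 months, and the protocol requires it for serious events. The protocol also places self-reports in a listing, so part of the conflict does not reach a by-arm percentage.

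Much of this stands. The loss is conditional on the last-dose reading and is confined to the treatment-period-plus-30-days table. But the other reading is equally available in the text, the 9-month table has the data gap in SAP 1.6, and SAP 6.1 also reports coded self-reports by preferred term for each randomized group.

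A reader might go further in three ways that the documents do not support.

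- **That about 64 days is the most that can be lost.** That figure is only the Day 20 case; the maximum is 83.
- **That a real harm would vanish.** The illustration rests on assumed inputs. At five times the hazard the difference is attenuated, not removed, and a 9-month by-arm table is also planned.
- **That the double-blind-period Cox models in SAP 5.4.2 suffer informative censoring at drug stop.** SAP 5.4.2 treats participants without an event in the analysis period as censored and sets no censoring at last dose. SAP 2.3.2 keeps data after discontinuation, SAP 2 speaks of the 12-week period, and each model is also run over the whole study. No SAP text uses Protocol 4.4 as a censoring rule.

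**Conclusion.** The inconsistency is real and sits in current text, both between the protocol and the SAP and within SAP 6.1. If the last-dose reading is programmed, a participant whose last dose is on Day d loses 84 - d days, at most 83 (80 to 86 with the visit window). The crude percentages in the treatment-period-plus-30-days table then compare unequal follow-up whenever early stopping differs by arm. Separately, the Day 87 rule cuts 27 days of self-reports for completers.

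The day counts follow from the documents alone. The effect on event percentages does not: shifts of roughly 0.3 to 1.5 points in the illustration depend on assumed risk, stopping day, stopping rates and hazard. With the 400 to 480 participants anticipated in SAP 1.4, 200 to 240 per arm, one percentage point is 2.0 to 2.4 participants in an arm. The primary endpoint is not affected. The point is worth settling before the by-arm safety tables are programmed, because the anchor should not be chosen with results in view.

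**What to change.** 1. Keep capture from informed consent for both sources. SAP 5.1.2 now starts self-report capture at first dose and should match the protocol.
2. For the main by-arm claims table, count events from first dose to Day 84 + 30 = Day 114, or to death or withdrawal of consent, for every dosed participant whatever the date of drug stop.
3. Add a supportive table ending at last dose plus 30 days, with person-time rates.
4. Use the Day 114 end for call-center capture and its listing, replacing the Day 87 limit in SAP 2.1.
5. Align the Synopsis, 1.3 footnote e, 3 and 8.3.1 in the protocol, and 1.6, 2.1, 5.1.2 and 6.1 in the SAP. In SAP 1.6, extend the pull of claims for events of interest to Month 9 so that the second table in SAP 6.1 can be produced.
6. As a clarification only, state in SAP 5.4.2 that the double-blind period is Day 1 to Day 84 for all participants.

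**Cost.** This is mainly protocol and SAP wording, plus a longer claims extract and one extra table. Claims arrive passively, and the protocol already captures them to the end of the study. The main table would include off-drug days for early stoppers, which the supportive table addresses. Making the last-dose table the main one would also be workable if stated, but then person-time rates would have to lead.

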optional participant satisfaction survey at end of study (via smartphone), step count and floors climbed (via the Fitbit device), medical and pharmacy claims data (including up to 36 months history for eligibility confirmation), HRU and health economics (including hospitalization/readmission due to HF or other reason, ED visits, the duration of stay at each hospitalization/readmission), review of claims for prohibited medications and new diagnoses that may require discontinuation, and adverse events. In addition, information related to outpatient IV diuretics, inotropes and vasodilators and in-patient IV therapies as well will be considered relevant. Note that claims data that involves up to 36 months history to confirm eligibility into this study will not be part of the study database for analysis.

Participants will be of any gender, 18 years of age or older, and will have clinically stable, symptomatic HF with or without type 2 diabetes mellitus (T2DM) with a KCCQ overall summary score <80 prior to randomization, which represents New York Heart Association (NYHA) II and III participants.

Figure 1: Schematic Overview of the Study

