2.7. Imputation Rules for Missing AE Date/Time of Onset/Resolution

Claims data are generally based on service dates and not on start and end dates for adverse events. Consequently, no imputation rule for missing AE dates can be applied.

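### Claims adverse events of interest have no rule separating new from pre-existing conditions, and the look-back claims that could supply one are kept out of the analysis database

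*SAP*

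**What the plan says.** On identification, SAP 6.1 says: "The claims data will utilize ICD codes to identify the SAEs and AEs of interest which are defined in the protocol". Neither document gives a code list, a code position, an encounter type, a first-occurrence rule or a claim-free period.

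On dates, SAP 6.1 assumes that the "claims database will have dates of service provided (procedure dates, office visits, hospital admissions, etc.) but not actual start/end dates of events", and SAP 2.7 agrees: "Claims data are generally based on service dates and not on start and end dates for adverse events". The service dates taken into account are those "starting from the time informed consent is signed until the end of double-blind treatment plus 30 days". SAP 2.1 adds that no time windows apply to claims safety data.

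On history, SAP 1.2 is explicit: "claims data that involves up to 36 months history to confirm eligibility into this study will not be part of the study database for analysis". SAP 1.6 is consistent with this: collection of "claims associated with AEs of special interest will begin on the Informed Consent Date through the End of Treatment + 30 days".

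On definitions, SAP 6.1 says: "A treatment emergent AE is defined as an event that occurs after the first dose of study intervention", and also admits events that get worse during double-blind treatment. Protocol Appendix 7 (10.7) limits adverse events to occurrences that are new, or worse or more frequent than at baseline.

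On output, SAP 6.1 plans numbers and percentages of participants with a serious event or event of interest, by arm and by diabetes status. It also plans a listing of events between consent and the day before first dose, without saying that those events are left out of the summaries.

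**The concern.** Both definitions turn on onset or worsening. Service-date claims show neither, and the SAP describes no severity information in claims. The data that could tell an old condition from a new one are the pre-consent claims, and the SAP keeps them out of the analysis. What is left in SAP 6.1 is a code on a service date in a window that opens at consent, not at first dose. An office visit to follow up a fracture, kidney injury or older amputation meets that description.

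This matters because SAP 6 bases the safety summaries on claims. Protocol 8.3 and 9.4.3 use claims to compare serious events and events of interest between groups, and after treatment plus 30 days claims are the only source of serious events. SAP 6.1 also rules out reconciliation with call-center reports, so a misclassified claim would not be caught that way. If old conditions enter the counts, the reported rates overstate incidence in both arms, and relative comparisons look closer to no difference than they should.

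**Working it through.** The documents give no adverse event rate, event count or safety power, so there is no stated figure to reproduce. The check has three parts.

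**1. Which categories are exposed.** Protocol 5.2 set against the listed events:

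| Category | Prior history excluded at entry | Left open |
|---|---|---|
| Diabetic ketoacidosis | Any history | Little |
| Lower limb amputation | Atraumatic, within 12 months | Older or traumatic |
| Hypotension | Diagnosis within 30 days | Older |
| Fracture, acute kidney injury, urinary and genital infection | No exclusion for a prior event | All prior events |

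The exclusion of major surgery within 3 months may remove some recent surgically treated fractures. SAP Appendix 4 plans a medical-history display, but nothing links it to event counting.

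**2. How much of the window precedes first dose.** The protocol schedule allows screening within 28 days before baseline and baseline within 7 days before Day 1. Treatment lasts 84 days and follow-up adds 30. The pre-dose share is at most (28 + 7) / (35 + 84 + 30) = 35/149 = 23%. If the 28 days are read as running to Day 1, it is 28/142 = 20%.

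**3. What carry-over does to a comparison.** Every rate here is assumed. Let the true risks be 2% and 4% (ratio 2.0, difference 2.0 points), and let p be the share of each arm counted only because of an old condition. It is taken as equal because allocation is randomized and blinded. The observed ratio is (4% + p)/(2% + p).

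| p | Observed risks | Ratio | Difference |
|---|---|---|---|
| 0% | 2% and 4% | 2.00 | 2.0 points |
| 1% | 3% and 5% | 5/3 = 1.67 | 2.0 points |
| 3% | 5% and 7% | 7/5 = 1.40 | 2.0 points |
| 5% | 7% and 9% | 9/7 = 1.29 | 2.0 points |

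If carry-over can fall on participants who also have a new event, the observed risk is c + (1 − c) × true risk. For c = 1%, 3% and 5% the ratios are 1.66, 1.39 and 1.28, and the difference shrinks only by the factor (1 − c), for example to 1.90 points at 5%.

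A second assumed case uses 240 per arm, half the upper end of the 400–480 total in SAP 1.4. True risks of 2% and 5% with c = 5% are observed as 6.9% and 9.75%. The ratio falls from 2.50 to 1.41 and the difference from 3.00 to 2.85 points. A two-sided 5% test would have about 43% power without carry-over and 20% with it, although no such test is planned. If a look-back rule caught all, 80% or 50% of the carry-over, with flagged participants left out of the denominator, the ratio would return to 2.50, 1.98 or 1.65.

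**The case against.** The other side has several fair points.

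- **Silence is not a rule.** A reader might infer that every coded visit in the window is to be counted as a new event. The SAP does not say so. It says codes will be used for identification and leaves claims mapping to data specifications that are not part of these documents. This stands. The defect is an unfilled step, combined with stated choices (no look-back data, window opening at consent) that leave the step hard to fill well.
- **The treatment-emergent definition is not unusable everywhere.** Start and end dates are assessed for call-center events, and a treatment-emergent listing of hospitalizations and deaths is planned. This stands. The difficulty is with diagnosis codes from other encounters.
- **Harm is not hidden.** A reader might infer that carry-over masks harm. With balanced carry-over the absolute excess stays visible, and SAP 6.1 plans percentages by arm, not risk ratios or tests. The documents support dilution of relative comparisons and no more.
- **This is not the only comparison by arm.** SAP 5.4.2 has Cox models for hospitalization and death, SAP 9 has Fisher exact tests for hospitalizations and emergency visits, and SAP 6.1 mentions self-reported events by preferred term and arm, although SAP 5.1.2 promises at most a listing.
- **Counting is per participant**, so repeat visits do not multiply the numbers. This stands.
- **A blanket washout could do damage.** The protocol's definition includes aggravation in frequency, so a uniform 12-month claim-free rule would drop recurrent infections or hypotension that can be genuine adverse events. This stands and shapes the fix.

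None of this supplies a way to keep a pre-existing condition out of the counts.

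**Conclusion.** The point holds in a limited form. As written, the SAP cannot separate old from new conditions in the claims counts of events of interest, although both its own treatment-emergent definition and the protocol's adverse event definition require it. The expected result is inflated rates in both arms and ratios drawn towards 1, with the risk difference little changed.

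The size is unknown. The ratios of 1.67, 1.40 and 1.29 rest on assumed true risks of 2% and 4%, on assumed carry-over of 1%, 3% and 5%, and on equal carry-over by arm. The effect will differ by category: least for ketoacidosis, partly limited for amputation and hypotension, and open for fracture, kidney injury and infections. Comparisons of rare events will be imprecise at 200–240 per arm in any case. The change is worth making because it is cheap and the affected table is the main summary of these events; it does not threaten the trial's primary conclusion.

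**What to change.** Amend SAP 1.2, 1.6 and 6.1 as follows.

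- Add the code list for each event category.
- Load look-back claims for those categories only. Confirm first that they are available in the claims vendor's feed and how complete they are per participant, since the history is up to 36 months, not a guaranteed length.
- In the main table, count the first qualifying claim dated on or after first dose.
- For fractures and amputations, use initial-encounter or procedure codes.
- For kidney injury and similar categories, require no claim in the same category during a fixed look-back before first dose.
- For categories that can recur (urinary and genital infections, hypotension), use a short category-specific claim-free gap so that true recurrences still count.
- State whether participants with a look-back claim stay in the denominator.
- Show pre-dose service dates only in the listing already planned.
- Keep the all-claims count as a supportive table.

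The cost is SAP wording, programming and a restricted extract. The protocol schedule (footnote d) already provides for collecting the history after consent, so participants carry no added burden. The downside is that some true recurrences inside the look-back leave the main table; they remain in the supportive one.
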